7.4 Reporting Procedures

Each clinical investigator is responsible for reporting serious or unexpected adverse events to the IRB at their institution and to the Safety Monitor. The Safety Monitor/Officer (currently DSMB Chair, [name]), DCC Biostatistician (currently [name]), and NIA Project Scientist or Program Officer are notified by email when a report of any serious adverse event is entered into the REDCap database. The Safety Monitor summarizes the case; if it is potentially related to the intervention, the Safety Monitor reports it to the NIA Program Officer and the remaining DSMB members in an expedited manner (i.e., within 24 hours of learning of these events). The Safety Monitor (currently [name]) will determine whether the case should be reported to the IRBs at all the institutions participating in the trial. The DCC summarizes all SAE’s, including those that are definitely not related to the intervention, for the DSMB at each DSMB meeting.

Approximately every 6 months, or more frequently upon request of the Chair of the DSMB, the DCC will summarize all adverse events (including serious, unexpected and expected) by randomization group in a report to the DSMB. In addition, the report will contain accrual and drop-out rates. The DSMB will summarize their findings to the NIA with approval to continue the clinical trial, or a recommendation to modify the trial or terminate the trial.

Further, in accord with Investigator-Initiated Research (IIR) clinical studies with Pfizer, all serious adverse events will also be submitted to Pfizer via their IIR SAE form; this applies to all subjects receiving a Pfizer product (i.e. Premarin cream) or blinded therapy and also includes those SAEs not study-drug-related. The clinical study reporting period begins from the time that the subject receives her first dose of Pfizer product (or blinded therapy) through and including 28 days after the last administration of the Pfizer product (or blinded therapy). The time frame for reporting the SAE to Pfizer is immediately upon awareness (if fatal or life-threatening SAE) or within 24 hours of first awareness (if not fatal or life-threatening). The PI will include a rationale and medical justification as an assessment of causality, i.e., the determination of whether there is a reasonable possibility that the Pfizer product (or blinded therapy) caused or contributed to an AE. Finally, new, updated, or corrected information about a previously-reported SAE will also be communicated to Pfizer in a follow-up report.

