6 STUDY PROCEDURES

See next page for Schedule of Evaluations (6.1)

PFD (Pelvic Floor Disorder) Questionnaires consist of 3 validated short-form (in English and Spanish) PFD questionnaires (already used as standard of care at patient intake): Pelvic Floor Distress Inventory (**PFDI-20**⁷³), Pelvic Floor Impact Questionnaire (**PFIQ-7**⁷³), Pelvic Organ Prolapse/ Urinary Incontinence Sexual Function Questionnaire (**PISQ-IR**⁷⁴) *plus* a 6-question survey of **vaginal atrophy symptomatology**⁷⁵, a general quality-of-life (QoL) instrument (**SF-12**), and a **body image questionnaire**.

Schedule of Evaluations (Table 1)Assessment	Baseline (≥5wk before Surgery)	Preop Visit (w/in 2wk of surgery)	Surgery/ Hospitalization	1mo Postop Visit (±2wk)**	3mo Postop Call (±2wk)	6mo Postop Visit (5-7mo)	9mo Postop Call (±2wk)	12mo Postop Visit (10-14mo)	18&30mo Postop Calls (±2wk)	24&36mo Postop Visits (±2mo)
Informed Consent Form, Inclusion/Exclusion, Randomization	X									
Demographics	X									
Medical History	X									
Exam: POP-Q	X			X		X		X		X
Exam: Levator muscle strength assessment	X	X		X		X		X		X
Exam: Vaginal atrophy assessment	X	X	X	X		X		X		X
Exam: vaginal epithelium/ granulation tissue assessment	X	X		X		X		X		X
Medication Review	X	X		X	X	X	X	X	X	X
PFD Questionnaires	X	X			X*	X	X*	X	X*	X
PGI-I and/or PGI-S	X					X		X		X
Vaginal Maturation Index	X		X					X		
Blood Serum (E1, E2)	X							X		
Blood (whole), storage for DNA/ genetics assessment (optional)	X									
Vaginal Wall Biopsy (optional)			X							
Study Cream ^{Tube No.} delivery/receipt	X ¹		X ²		X ³	X ⁴	X ⁵			
Medication Calendar ^{Tube No.} collection		X ¹			X ²	X ³	X ⁴	X ⁵		
Preop History/Exam		X								
Postop Med/Surg update				X	X*	X	X*	X	X*	X
Postop Extra Treatment				PRN	PRN	PRN	PRN	PRN	PRN	PRN

Adverse Event, Protocol Deviation forms	PRN	PRN	PRN	PRN	PRN	PRN	PRN	PRN	PRN	PRN
---	-----	-----	-----	-----	-----	-----	-----	-----	-----	-----

POP-Q, pelvic organ prolapse quantification examination; PFD, Pelvic Floor Disorder; PGI-I and –S, Patient Global Impression of Improvement, - Severity; E1, estrone; E2, estradiol

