- Patient Global Impression of Severity (PGI-S) and Patient Global Impression of Improvement (PGI-I) (**Form 11**): 1-question tools assessing overall impression of symptom severity and improvement related to POP.
- Postop Medical/Surgical History update (**Form 15**)
- Postop Exam (**Form 16**)
- Postop Extra Treatments (**Form 17**): as needed

9-month Postoperative Phone Call (± 2 wk):

- Postop phone call documentation (**Form 18**) completed, with follow-up questions about feelings of vaginal pressure/ bulging and if there has been treatment for prolapse since the last study visit.
- Study cream Tube #5 is dispensed to the subject via FedEx with instructions to continue twice-weekly application.
- Medication Calendar (**Form 07**) documenting use of Tube #4 (6mo-to-9mo) is collected either by mail or fax (or reminder to bring calendar to 12mo Postop Visit). Reminder to bring Study cream Tubes #4 and #5 to next appointment.
- Medication Review (**Form 05**): *updated from 6-month Postop Visit*
- Postop Extra Treatments (**Form 17**): as needed
- Adverse Events (**Form 09**) and Protocol Deviation (**Form 21**): as needed

12-month Postoperative Visit (± 2 mo):

- Study cream Tube #5 is collected (and #4, if not previously collected) (**Form 07**). The weight of Tubes #4 and #5 are documented and the tubes

appropriately disposed/destroyed.

- Medication Calendar documenting use of Tube #5 (9mo-to-12mo) is collected (**Form 07**).
- Medication Review (**Form 05**): *updated from 9-month Postop Call*
- Adverse Events (**Form 09**) and Protocol Deviation (**Form 21**): as needed
- Pelvic Floor Disorder (PFD) Questionnaires (**Form 10**)
- Patient Global Impression of Severity (PGI-S) and Patient Global Impression of Improvement (PGI-I) (**Form 11**)
- Postop Medical/Surgical History update (**Form 15**)
- Postop Exam (**Form 16**)
- Postop Extra Treatments (**Form 17**): as needed
- Specimen collection, preparation, and shipment to UTSW: blood/serum (sent on cold packs within 24 hr of collection *or* store at -20°C and ship on dry ice) and VMI (store at 4°C and ship on cold packs)

18-month Postoperative Phone Call (±2wk):

- Postop phone call documentation (**Form 18**) completed, with follow-up questions about feelings of vaginal pressure/ bulging and if there has been treatment for prolapse since the last study visit.
- Medication Review (**Form 05**): *updated from 12-month Postop Visit*
- Postop Extra Treatments (**Form 17**): as needed

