7.3 Adverse Events and Serious Adverse Events

Definitions:

- An **adverse event (AE)** is defined as any unfavorable and unintended diagnosis, symptom, sign (including an abnormal laboratory finding), syndrome or disease which either occurs during the study, having been absent at baseline, or if present at baseline, appears to worsen. Adverse events will be recorded regardless of their relationship to the study intervention (**Form 09**).
- A **serious adverse event (SAE)** is defined as any untoward medical occurrence that results in death, is life threatening, requires inpatient hospitalization or prolongation of existing hospitalization, results in persistent or significant disability/incapacity, or is a congenital anomaly (**Form 09b**).

No pre-specified laboratory measures will be collected to assess safety.

These AE's will be collected as *solicited events* (**Forms 09, 12, 13, 14, 15**):

- Vaginal or vulvar complaints possibly associated with vaginal estrogen cream: itching, irritation, vaginal or vulvar rash, yeast infection or other discharge.
- Non-vaginal complaints anticipated with the use of vaginal estrogen cream: breast tenderness, joint aches, headache.
- Intraoperative AE's: bladder perforation, ureteral injury, urethral injury, rectal injury, other bowel injury, major vascular injury, anesthesia-related complications.
- AE's encountered during hospitalization after surgery: blood transfusion, wound complications, febrile or dermatologic complications, organ damage complications, cardiovascular complications, pulmonary complications, gastrointestinal complications, neurological complications, other.
- AE's encountered or reported at postoperative visits: vaginal or vulvar complaints (as above)/ non-vaginal complaints (as above) possibly related to estrogen

application, wound complications, febrile or dermatologic complications, neurological complications, other.

Case report forms (**Forms 09, 13, 14, 15**) all offer lines for data entry for “other” events, and Form 09 gives a reminder as to events triggering a SAE designation (**Form 09b**).

Possible safety issues or adverse events are queried and inventoried at all follow-up appointments and calls.

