7.5 Follow-up for Adverse Events

The PI and biostatistician at UTSW will be responsible for:

- maintaining an appropriate log of data regarding these events
- monitoring the course of the event to resolution or the end of the trial

- notifying all site investigators of all serious adverse events for appropriate reporting to their local Institutional Review Boards
- reviewing updated blinded, aggregate data summarizing participant safety. These reports will include incidence, severity, and relatedness to treatment of all reported and treatment emergent Adverse Events and withdrawals from the trial due to Adverse Events.

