9.3 Interim analyses and Stopping Rules

No analyses of efficacy are planned to be presented until the end of the trial. Additional DSMB review may be requested by the UTSW PI and biostatistician, and an emergency review by the DSMB requested at any time if questions of participant safety arise. Between-groups comparisons of safety variables will be presented to the DSMB.

Should the DSMB decide to issue a recommendation to terminate or alter the study protocol based on safety, futility, or poor study performance (e.g., slow accrual, high loss-to-follow-up, poor quality control) a full vote of the 3 site PI's will be required. Examples of findings that might trigger a safety review are the number of SAEs overall, the number of occurrences of a particular type of SAE, severe AEs/reactions, or increased frequency of events. Such findings are presented to the study biostatistician or to the Data and Safety Monitoring Board (DSMB) statistician to review the events by group to determine whether there are statistical as well as clinical concerns. The statistician reports the findings to a closed session of the DSMB or to the Safety Officer and/or NIA. The findings are used to determine what steps will be taken.

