9.5 Data Analyses

Aim 1. The **primary outcome** will be analyzed according to the assigned treatment group (modified intention-to-treat): i.e., all participants that are randomized *and* undergo a surgical prolapse repair *and* have at least one postoperative assessment will be analyzed according to their randomized assignment group. All eligible subjects who consent to the study and are enrolled will be available for analysis of baseline characteristics, and those that are randomized and use their study drug will be monitored for adverse events, but they must meet the additional qualifications above (i.e., undergo surgery and have a postoperative assessment) to be analyzed for the primary study outcome. At baseline, continuous measures will be compared between groups with Student's t-test and chi-square (or Fisher's exact test) for categorical measures. Scores from repeated surveys are continuous outcomes data and will be analyzed using repeated measures analysis of variance. We will test for interactions between time effect and treatment effect. For categorical data (e.g. prolapse stage), the analysis will be by categorical data modeling using weighted least squares and mixed logit models, with cross-sectional assessments (at specific time intervals) by chi-square. For missing follow-up points there are two possible approaches: (i) if there are few missing follow-up points, then their values may be imputed through multiple imputation methods, in which case repeated measures analysis of variance may be used following multiple imputation; (ii) more likely, we will make time a random effect and a mixed effects model with repeated measures will be applied. Time-to-event or event-free-time will be analyzed using survival methods to include the log-rank test and Cox regression. For measures that may not be assumed normal, the data will be transformed using a rank transformation prior to analysis.

In accordance with NIH policy, we will include an analysis of the intervention effect (CE cream) performed by racial/ethnic subgroups, recognizing that the analyses will not have high statistical power for detecting clinically meaningful differences between races/ethnicities.

Aim 2 Outcomes. As above, continuous scores from repeated surveys will be analyzed using repeated measures analysis of variance with appropriate corrections made, as necessary, for missing data.

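### By-arm adverse event summaries draw on collection to 36 months although cream stops at about 12 months, and no by-arm table is limited to or split by the treatment period

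*Combined protocol and SAP*

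**What the plan says.** **Scope of the tables.** Under section 7.4, roughly twice a year, "the DCC will summarize all adverse events (including serious, unexpected and expected) by randomization group in a report to the DSMB". Section 9.3 states: "Between-groups comparisons of safety variables will be presented to the DSMB". Neither gives a time window.

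**Time scope of an AE.** Section 7.3 counts any unfavourable finding "which either occurs during the study, having been absent at baseline", or one present at baseline that worsens. It says that "adverse events are queried and inventoried at all follow-up appointments and calls". Section 6.2.3 lists the AE form at the 18-, 24-, 30- and 36-month contacts.

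**Time on cream.** The Précis and section 3 plan 6 to 8 weeks before surgery and one year after it. At the 12-month visit "Study cream Tube #5 is collected (and #4, if not previously collected". Table 1 in section 6 allows a range for that visit: "12mo Postop Visit (10-14mo".

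**Treatment-emergent events.** The term appears once, in section 7.5, where a blinded aggregate review covers "incidence, severity, and relatedness to treatment of all reported and treatment emergent Adverse Events". It is not defined.

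**Analysis section.** Section 9.5 says that "those that are randomized and use their study drug will be monitored for adverse events". That identifies who is observed, but gives no AE analysis or window.

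**The one exposure-based window.** Section 7.4 uses first dose to 28 days after last dose, but only for reporting serious events to the drug supplier.

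**The concern.** A woman who completes the study spends roughly 13 to 14 months on cream and about 24 months off it, with AEs recorded throughout. If cream causes an excess, it should appear mainly while cream is used. Events after cream stops would be expected about equally in the two arms, so pooling both periods adds the same background to each. The ratio moves towards 1 and the comparison becomes noisier.

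At stake is how clearly later DSMB reports, and the safety tables made after the code break, would show an on-cream excess if one exists. The 3-year DSMB report still bears on women being dosed. The efficacy analysis is not affected.

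**Working it through.** The plan states no AE rate target, safety power or exposure figure, so there is nothing of its own to reproduce. The question is how far a cumulative all-AE table would shift a ratio.

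**Inputs from the documents.** Accrual is uniform over 36 months (9.2). There are 222 women, 111 per arm (Précis), with 15% lost between baseline and surgery (9.2). Cream runs for 12 months after surgery and AE collection for 36. The code break comes once all women reach one year (9.2.1).

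**Assumptions.** The pre-operative phase is 7 weeks, or 1.61 months (using 6 or 8 weeks moves results by at most 0.01). Tables are cumulative. There is no carry-over after cream stops. The true on-cream rate ratio R is 2.0, chosen only for illustration. Background after month 12 is b times the on-cream background (b = 1, 0.5 or 0.25, since surgical events cluster early). A share d leaves at 12 months (0 or 25%).

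**Formula.** Observed ratio = 1 + (R − 1) × on / [on + b(1 − d) × off], where on and off are mean months per woman at the time of the report.

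**Exposure.** Full on-cream time is 1.61 + 12 = 13.61 months.
- 24 months from first enrolment: on = (13.61²/2 + 13.61 × 10.39)/24 = 9.75; off = 10.39²/(2 × 24) = 2.25.
- 36 months: on = (13.61²/2 + 13.61 × 22.39)/36 = 11.04; off = 22.39²/(2 × 36) = 6.96.
- Code break (36 + 13.61 = 49.6 months): on = 13.61; off, capped at 24, = (24²/2 + 24 × 12)/36 = 16.
- Study end: on = 13.61; off = 24.

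| Table | b=1, d=0 | b=0.5, d=0 | b=0.25, d=0.25 |
|---|---|---|---|
| 1-year DSMB report | 2.00 | 2.00 | 2.00 |
| 2-year DSMB report | 1.81 | 1.90 | 1.96 |
| 3-year DSMB report | 1.61 | 1.76 | 1.89 |
| Code break | 1.46 | 1.63 | 1.82 |
| Study end | 1.36 | 1.53 | 1.75 |

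For example, study end with b=1 and d=0 is 1 + 13.61/37.61 = 1.36. With b=0.25 and d=0.25 it is 1 + 13.61/(13.61 + 0.1875 × 24) = 1.75.

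**Alternative: events follow contacts, not time.** There are 7 contacts on cream (pre-op, surgery, 1, 3, 6, 9 and 12 months) and 4 after. Study end gives 1 + 7/11 = 1.64. At the code break the mean number of later contacts is (30 + 24 + 18 + 12)/36 = 2.33, giving 1 + 7/9.33 = 1.75.

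**Counts, risks and power.** With equal off-cream rates, the expected difference in event counts is the same in either table. Take an assumed placebo on-cream risk of 10%, R = 2, a constant background, 111 per arm and two-sided 5%. The on-treatment comparison is 10.0% v 19.0% (difference 9.0 points, risk ratio 1.90, power about 48%). The 36-month comparison is 25.3% v 32.7% (difference 7.5 points before rounding, risk ratio 1.30, power about 23%).

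**Women still on cream at 36 months.** 222 × 13.61/36 = 84. With 15% lost at surgery, 222 × 1.61/36 + 0.85 × 222 × 12/36 = 73. The number is lower again if the 25% loss or non-adherence in 9.2 is counted.

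**The case against.** **Cumulative pooling is inferred.** Section 7.4 does not say that each report accumulates from first enrolment or merges phases. A reader might infer that the plan commits to pooled 36-month tables. The text implies it but does not state it, and every diluted ratio above depends on it.

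**The low ends need strong assumptions.** The values 1.36 and 1.46 need full retention and a late background equal to that of a period containing major surgery. Section 4.1 requires availability for only one year. If half left at 12 months with b = 0.25, the study-end figure would be 1 + 13.61/(13.61 + 3) = 1.82. The ranges are illustrative.

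**No excess is documented.** Section 7.2 reports discharge, headache and joint aches as no more frequent on cream than placebo. Its any-AE figures from another study, 55% v 47%, give a ratio of about 1.17, which by the formula would read 1.08 to 1.14 at the code break. For effects listed at 2 to 3%, a doubling is about 6 women v 3, and no window would settle that.

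**Safeguards exist.** Potentially related serious events go to the DSMB on an expedited basis (7.4). Reports are split by seriousness and relatedness, and the DSMB approves and may modify the format (7.6). A reader might infer that a real harm would be missed; the documents do not support that. These safeguards still leave open which events enter the arm comparison.

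**Post-cream events can be informative.** Section 2.2c describes a burst of protease activity after estrogen withdrawal in mice, so late events may differ by arm. This stands, and it is why the full-period view should not be discarded.

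**The treatment-emergent wording is not the cause.** A reader might infer that the undefined term drives the by-arm problem. It sits in a blinded aggregate review, and its start is largely implied because AEs are judged against baseline. The missing end is worth fixing, but it is a side issue.

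**Conclusion.** The concern holds as a minor point. The plan calls for by-arm summaries of all AEs, collects them for about two years after cream stops, and limits or splits no by-arm table by treatment period. If the tables are cumulative, an assumed on-cream ratio of 2.0 would read about 1.6 to 1.9 in the 3-year DSMB report and about 1.4 to 1.75 at study end, with lower power. First-year reports are unaffected. The expected difference in event counts is unchanged, and the risk difference shrinks less than the ratio does.

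The figures rest on uniform accrual, no carry-over, the stated ranges for late background and retention, and a ratio chosen for illustration. They do not show that cream causes harm. Code-break and study-end tables concern interpretation only, since planned cream use has ended or is ending by then.

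**What to change.** In sections 7.4, 9.3 and 9.5, add a by-arm on-treatment AE table in all randomised women who used any cream. The window runs from first application to the end of planned treatment plus 28 days. Planned treatment ends at the 12-month visit, or at 12 months if that visit is missed. For women who never have surgery it ends when cream is returned or stopped. Use the same window to define *treatment emergent* in 7.5.

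Keep the full 36-month by-arm table, or a separate post-treatment table, for late or withdrawal effects.

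As a sensitivity analysis, end the window 28 days after last application. This should not be the main window, because non-adherence differed by arm in the pilot (4 of 13 on estrogen v 0 of 13 on placebo, section 2.2a).

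Some dilution remains. With 28 days = 0.92 months, a true 2.0 reads 1 + 13.61/14.53 = 1.94 if cream is used to a month-12 visit. It reads 1 + 13.61/16.53 = 1.82 if cream stops at month 12 but the visit is at month 14.

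The cost is wording and programming before the code break, with no new visits: one or two extra tables, and fewer events in the on-treatment table. It relies on AE onset date (the form's fields are not shown, so this is assumed) or, failing that, the visit at which the event was first recorded.

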7.5 Follow-up for Adverse Events

The PI and biostatistician at UTSW will be responsible for:

- maintaining an appropriate log of data regarding these events
- monitoring the course of the event to resolution or the end of the trial

- notifying all site investigators of all serious adverse events for appropriate reporting to their local Institutional Review Boards
- reviewing updated blinded, aggregate data summarizing participant safety. These reports will include incidence, severity, and relatedness to treatment of all reported and treatment emergent Adverse Events and withdrawals from the trial due to Adverse Events.

7.6 Safety Monitoring

The NIA has appointed a Data Safety Monitoring Board (DSMB), which will regularly evaluate the safety of the participants in IMPROVE. The IMPROVE UTSW PI and Biostatistician will be blinded to treatment allocation using dummy treatment group assignments while the DSMB and statistician/ programmer will be unblinded. The DSMB will consist of a chairperson and 2 other individuals who have expertise in clinical study design/ conduct and biostatistics. All board members will be independent of the institutions and investigators participating in the trial and have no financial ties to Pfizer (maker of Premarin® vaginal cream) or to the outcome of the trial.

The DSMB will review the study design and plans for recruitment, adherence, interventions, data quality and safety monitoring. The responsibilities of the DSMB are to:

- evaluate the safety of trial participants
- ensure confidentiality of data and the results of monitoring
- report to the UTSW PI and biostatistician on the safety of participants
- make recommendations on continuation, termination, or modifications to the trial

DSMB Process: There will be 2 sections of the DSMB meeting: open and closed. In the open section of the meeting, the PI and Biostatistician will present the report to the DSMB and answer questions. The closed section of the meeting will include the members of the DSMB only.

Reports to the DSMB, DSMB Review and Recommendations: The format of the report will be developed by the UTSW PI and biostatistician and approved by the DSMB. Additions and other modifications to the report may be directed by the DSMB. Interim DSMB reports generally consist of baseline characteristics, adverse events, serious adverse events and listings of extended evaluations by urogynecologists, if indicated, presented by dummy treatment group assignment. Adverse events will be categorized by seriousness and investigator-determined relationship to study drug. Data files to be used for interim analyses will have undergone established editing procedures to the extent possible, but all data, both edited and unedited, will be used to prepare interim reports. An unblinded statistician/ programmer will provide the dummy treatment group assignments to the IMPROVE biostatistician. In addition, the unblinded statistician/ programmer will prepare a confidential, sealed envelope to be included with the DSMB report using the real treatment assignment and an administrative assistant not associated with IMPROVE will mail the report one week in advance of the DSMB meeting. No other personnel at UTSW will have access to the real treatment assignment codes. The reports to the DSMB will be numbered and provided in sealed envelopes within an express mailing package to maintain confidentiality. All DSMB reports are confidential. A copy of the report will be retained in

a locked, confidential file at the Coordinating Center. After each review, the DSMB will send a brief letter to the UTSW PI and biostatistician that contains a recommendation to continue, terminate, or alter the study.

Access to Interim Data: Access to the accumulating safety and outcome data will be limited to as small a group as possible.

Confidentiality: All materials and proceedings of the DSMB are completely confidential.

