9.2.1 Treatment Assignment Procedures

A randomized, double-blind, placebo-controlled trial design (CE cream versus placebo) will be used in this study. SAS V9.3 will be used by the study biostatistician to generate the stratified, randomization lists. Patients will be stratified by site, hysterectomy status, and duration since menopause (<10 and ≥10 years). The randomization lists will be distributed to each site’s research pharmacy (or their designee). Those conducting the primary and secondary measurements as well as the patients will be blinded to treatment assignment. These data will *not* be housed in study’s database (i.e. REDcap®).

At the discretion of the primary investigators at any of the clinical sites, they may request the primary site PI to have the blind broken. The primary site PI—likely in consultation

with the Safety Monitor, as needed—will then request this information of the DCC study database manager (permitting [name] to remain blinded) if it is clinically needed to understand the medication that the patient is receiving. It is anticipated that this would only be requested for important medical reasons, e.g., a serious adverse event or significant allergic reaction to study cream. In most cases, patient skin irritation with cream application could prompt discontinuation of the study medication without unmasking. There is no plan for clinical site research pharmacists to unmask participants, research coordinators, or local site PIs directly. Planned breaking of the randomization codes will only be after all participants have reached the primary study outcome time point one year postoperatively; there are no plans for interim/ early data analyses.

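### Presenting safety data by dummy arm in the open DSMB session, while code-break requests run through the same PI, could let the PI infer which label is estrogen

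*Combined protocol and SAP*

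**What the plan says.** Section 7.6 states who is masked and how: "The IMPROVE UTSW PI and Biostatistician will be blinded to treatment allocation using dummy treatment group assignments". The DSMB and a separate statistician/programmer are unblinded.

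The same section gives the interim report's usual content as baseline data, AEs, SAEs and, where indicated, listings of extended urogynecologist evaluations, "presented by dummy treatment group assignment". The unblinded "programmer will provide the dummy treatment group assignments to the IMPROVE biostatistician". The PI and biostatistician then present: "In the open section of the meeting, the PI and Biostatistician will present the report to the DSMB". A version with the real assignments goes to the DSMB in a sealed envelope, and 7.6 says nobody else at UTSW has the real codes.

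Section 7.5 makes the PI and biostatistician responsible for the event log, for following each event to its end, and for "reviewing updated blinded, aggregate data summarizing participant safety".

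Section 9.2.1 covers unmasking. Site investigators apply to the primary site PI: "they may request the primary site PI to have the blind broken". That PI "will then request this information of the DCC study database manager", an arrangement said to keep one named person (name removed) blind. The examples given are an SAE or a marked allergic response to the cream.

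Section 9.3 says of findings that might trigger a safety review: "Such findings are presented to the study biostatistician or to the Data and Safety Monitoring Board (DSMB) statistician", for examination by group.

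**The concern.** A dummy label protects the blind only while nobody who sees the labelled tables also learns the true arm of someone in them. Here one person, the PI, presents the labelled tables, shares responsibility for the event log, and is the channel for code-break requests. The events expected to prompt a request are of the kind the report splits by dummy arm. The weakness therefore lies in the procedure and needs no misconduct.

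At stake is the PI's blind. Under 4.3 the PI may approach and consent patients. Under 7.4 the PI writes the causality rationale for SAEs sent to the drug supplier. Under 9.3 the three site PIs must vote if the DSMB recommends stopping or altering the study. Someone with that discretion should not be able to work out which safety column is estrogen.

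**Working it through.** The plan states no figure on this point, so the check traces who sees what.

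**Step 1. Label information.** The PI and biostatistician see AE and SAE data by dummy arm in each report they present (7.6). Under 7.4 reports come about every six months.

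**Step 2. Recognising an event.** The same two people keep the event log (7.5) and the PI judges SAE causality (7.4). In a trial of 222 women, a distinctive event could be placed in one column of a summary table. It need not be: 7.4 describes AEs and SAEs as summarised, and the only listings named in 7.6 are of extended urogynecologist evaluations.

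**Step 3. Real-arm information.** The PI asks the database manager for the assignment (9.2.1). The text does not say who receives the answer. It may go to the PI, to the treating provider, or to both.

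**Step 4. The inference.** With two arms and two labels there are 2 possible mappings: A = estrogen with B = placebo, or the reverse. One woman whose true arm and dummy label are both known rules out one of them, leaving 2 − 1 = 1. If labels are constant across reports, that mapping applies to every report. The documents do not say whether labels are constant or are reassigned.

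**Step 5. How often a code break might occur.** The documents give no rate. As an illustration only, with assumed probability p per participant, independent across 222 participants, P(at least one) = 1 − (1 − p)^222:

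| Assumed p | P(at least one code break) |
|---|---|
| 0.2% | 36% |
| 0.5% | 67% |
| 1% | 89% |
| 2% | 99% |

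This is the chance of a code break, not of decoding. Decoding also needs the conditions in steps 2 to 4.

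**Step 6. Real codes.** Section 7.6 confines them at UTSW to the unblinded statistician/programmer. Section 9.2.1 has the coordinating center's database manager supply them on the PI's request. The two agree only if those roles are held by the same person, which is not stated.

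**The case against.** Several objections stand, and they set the limits of the point.

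- **Both people decoded.** A reader might infer that one code break unmasks the PI and the biostatistician together. Section 9.2.1 appears designed to keep one named person out of that loop, probably the biostatistician. By this route that person learns the label only if told.
- **Decoding is automatic.** It is not. No patient-level SAE listing is described, label constancy is not stated, and the recipient of the code is not named. Section 9.2.1 also presents unmasking as rare, and says skin irritation would usually be handled without it.
- **7.5 contradicts 7.6.** Totals by masked label are both blinded and aggregate. Section 7.5 does not say pooled over arms, so no contradiction is shown.
- **9.3 gives the study biostatistician real codes.** It does not say so. Review by group may mean dummy groups, as in 7.6. The wording is loose, but it does not show unblinding.
- **The primary outcome is compromised.** The documents do not support this. Knowing which label is estrogen does not tell the PI each woman's arm, because the participant-level dummy assignments go to the biostatistician. Patients and outcome assessors are blinded (4.3, 9.2.1), and no efficacy analysis is to be presented before the end of the trial (9.3).

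It can also be said that dummy labels are the plan's chosen masking device and that the DSMB approves the report format. That is so, but neither fact separates the labelled tables from the person who handles code-break requests. No provision reassigns labels, removes an unmasked case from the by-arm tables, or protects the PI as the named person is protected.

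**Conclusion.** The point holds in conditional form. The PI could infer which dummy label is estrogen if (a) the PI learns an unmasked participant's arm, (b) her event can be recognised in a dummy-arm column, and (c) the labels stay the same across reports. Condition (b) is plausible, since the expected triggers are of the kind the report shows and the PI shares the log. The documents leave (a) and (c) open.

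The consequence is limited to the label in the safety tables, plus the arm of the unmasked woman herself and of any other woman recognisable in those tables. Any resulting bias in the treatment comparison cannot be computed, and none is claimed. The change is still worth making: the exposure is avoidable, and the DSMB, which already receives the real assignments, loses no information.

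**What to change.** 1. In 7.6, make the open-session report pooled over arms. A code break then reveals one participant and nothing about the tables.
2. Put every by-arm table and listing, dummy or real, in the closed report prepared solely by the unblinded statistician/programmer. The biostatistician then no longer needs the dummy assignments for interim reports.
3. In 9.3, direct by-group review of events only to the unblinded statistician or the DSMB statistician, and remove the study biostatistician as an alternative.
4. Reconcile 7.6 and 9.2.1 on who at UTSW may hold real codes, and state in 9.2.1 who receives the assignment after a code break.

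**Cost.** The report must be re-laid out and a few sentences changed. The unblinded programmer and the sealed real-assignment version already exist. The real loss is that the PI and biostatistician can no longer discuss by-arm safety tables with the DSMB. As 7.6 admits only DSMB members to the closed section, the plan should also say how members put questions on those tables to the unblinded statistician/programmer.
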